### **10.3. Statement of the Null and Alternate Hypotheses**

#### **10.3.1. Primary Efficacy Endpoint**

The primary efficacy endpoint in this study is:

- Percent of patients who are considered complete responders, defined as complete resolution of spasms and hysarrhythmia or a pattern of epileptic encephalopathy

confirmed by 24-hour video-EEG from Day 13 to Day 14, as determined by the Independent Central Reader.

*Null hypothesis: There is no difference in the percent of patients defined as complete responders between treatment groups.*

*Alternative hypothesis: Treatment groups have significantly different percent of complete responders.*

### 10.3.2. Secondary Efficacy Endpoints

Secondary efficacy endpoints:

- Percent of patients with absence of infantile spasms as assessed by 24-hour video-EEG from Day 13 to Day 14 (partial response).

*Null hypothesis: There is no difference in the percent of patients with absence of infantile spasms between treatment groups.*

*Alternative hypothesis: Treatment groups have significantly different percentage of patients with absence of infantile spasms.*

- Percent of patients with absence of hypsarrhythmia or pattern of epileptic encephalopathy as assessed by 24-hour video-EEG from Day 13 to Day 14 (partial response).

*Null hypothesis: There is no difference in the percent of patients with hypsarrhythmia or pattern of epileptic encephalopathy at Baseline but absence of hypsarrhythmia or pattern of epileptic encephalopathy at Day 13 to Day 14 between treatment groups.*

*Alternative hypothesis: Treatment groups have significantly different percent of patients with hypsarrhythmia at Baseline but absence of hypsarrhythmia at Day 14 to Day 15.*

- Investigator impression of efficacy and tolerability of study drug (CGI-I) at End of Study/Early Withdrawal (Visit 5).

*Null hypothesis: There is no difference in the mean CGI-I score between treatment groups.*

*Alternative hypothesis: Treatment groups have significantly different mean CGI-I score.*

- Percent reduction in spasm-free days between the Initial Treatment Period (Days 1 to 14) and Screening Period (Days -14 to -1), as determined by the seizure diary entries.

*Null hypothesis: There is no difference in the percent reduction in spasm-free days between treatment groups.*

*Alternative hypothesis: Treatment groups have significantly different percent reduction in spasm-free days.*

- For patients with a complete response during the Initial Treatment Period who continue: percent of patients who relapse during the Extended Treatment Period confirmed by video-EEG following parent report of relapse, and time to relapse.

1. *Null hypothesis: there is no difference in the relapse rate between Vigabatrin + Placebo Responders and Vigabatrin + CBD Responders.*  
*Alternative Hypothesis: The relapse rate is different Vigabatrin + Placebo Responders and Vigabatrin + CBD Responders.*
  2. *Null hypothesis: there is no difference in time to relapse between Vigabatrin + Placebo Responders and Vigabatrin + CBD Responders.*  
*Alternative Hypothesis: The time to relapse is different Vigabatrin + Placebo Responders and Vigabatrin + CBD Responders.*
- For patients with partial response during the Initial Treatment Period who continue: percent of patients who achieve complete response during the Extended Treatment Period, confirmed by video-EEG following parent report, and time to complete response.
    1. *Null hypothesis: there is no difference in the percentage of patients achieving complete response in the Extended Treatment Period between Vigabatrin + Placebo Partial Responders and Vigabatrin + CBD Partial Responders.*  
*Alternative Hypothesis: The percentage of patients achieving complete response in the Extended Treatment Period is different Vigabatrin + Placebo Partial Responders and Vigabatrin + CBD Partial Responders.*
    2. *Null hypothesis: there is no difference in time to complete response between Vigabatrin + Placebo Partial Responders and Vigabatrin + CBD Partial Responders.*  
*Alternative Hypothesis: The time to complete response is different Vigabatrin + Placebo Partial Responders and Vigabatrin + CBD Partial Responders.*

#### **10.4. Subgroup Analyses**

No subgroup analysis is planned. However, if significant differences in efficacy endpoints are observed between developmentally normal vs. delayed patients, stratified analysis will be performed.

#### **10.5. Multiple Comparisons and Multiplicity**

No multiple comparisons are planned for analysis of the Primary Efficacy Endpoint. Secondary Endpoints will have an FDR correction applied to control the overall  $q = 0.05$ .

#### **10.6. Analysis of the Primary Efficacy Endpoints**

The primary efficacy endpoint will be assessed on the ITT population.

##### **10.6.1. Primary Efficacy Analysis**

The primary efficacy endpoint in this study is:

- Percent of patients who are considered complete responders, defined as complete resolution of spasms and hypsarrhythmia or a pattern of epileptic encephalopathy.

The percent of complete responders will be calculated for each treatment group and compared using Fisher's exact test.

#### **10.6.2. Presentation of the Primary Efficacy Results**

Percent of patients considered complete responders in each treatment group will be reported in a table. The p-value for difference between groups will be presented.

### **10.7. Analysis of the Secondary Efficacy Endpoints**

#### **10.7.1. Secondary Efficacy Endpoints**

The secondary efficacy endpoints in this study are:

- Percent of patients with resolution of infantile spasms as assessed by 24-hour video-EEG from Day 13 to Day 14 (partial response).
- Percent of patients with resolution of hypsarrhythmia or pattern of epileptic encephalopathy as assessed by 24-hour video-EEG from Day 13 to Day 14 (partial response).
- Investigator impression of efficacy and tolerability of study drug (CGI-I) at Visit 5 (End of Study) or Early Withdrawal.
- Percent reduction in spasm-free days between the Initial Treatment Period (Days 1 to 14) and Screening Period (Days -14 to -1), as determined by the seizure diary entries.
- For patients with a complete response during the Initial Treatment Period who continue: percent of patients who relapse during the Extended Treatment Period confirmed by video-EEG following parent report of relapse, and time to relapse.
- For patients with partial response during the Initial Treatment Period who continue: percent of patients who achieve complete response during the Extended Treatment Period, confirmed by video-EEG following parent report, and time to complete response.

Percentage of patients with partial response will be compared for each endpoint between treatment groups using Fisher's exact test.

Parent impression of efficacy and tolerability as measured by Clinical Global Impression – Global Improvement Scale (CGI-I) will be summarized by visit and status of response (complete/partial and no response). Appropriate summary statistics will be displayed and the CGI-I will also be analyzed as a continuous scale:

- 1 = Very much improved
- 2 = Much improved
- 3 = Minimally improved
- 4 = No change

5 = Minimally worse

6 = Much worse

7 = Very much worse

Percent reduction in spasm-free days, will be calculated for each treatment group. Treatment groups will be compared using ANCOVA with baseline number of spasm-free days as a covariate.

Percent of Responders who relapse and Partial Responders who achieve complete response during the Extended Treatment Period will be compared between treatment groups using Fisher's exact test. Time to relapse and time to complete response will be visualized using Kaplan-Meier curves and compared with log-rank tests.

### **10.7.2. Presentation of the Secondary Efficacy Results**

Percentage of Partial Responders at Day 14 will be summarized by treatment group and developmental stage, and the p-value presented. CGI-I results will be summarized as a frequency table and the mean and median score with the p-value. Percent change in spasm-free days, relapse rate, and rate of partial to complete response will be summarized by treatment group and p-value. Time to relapse and time to complete response will be presented by treatment group as Kaplan-Meier curves and p-value for log-rank test.

### **10.8. Summary of Reasons for Efficacy Non-evaluability/Exclusion from Efficacy Analyses**

If any patient is excluded from either the Safety or ITT Population, these will be presented in a listing with the reason for exclusion.

## **11. SAFETY AND TOLERABILITY**

### **11.1. Overall Summary of Tolerability**

The secondary objective of the study is to evaluate the safety and tolerability of Cannabidiol Oral Solution as adjunctive therapy with either vigabatrin or ACTH as initial therapy in treating patients with Infantile Spasms. This objective will be met by assessment of the following:

- Treatment-emergent AEs (TEAEs) and SAEs graded according to the Medical Dictionary for Regulatory Activities (MedDRA version 19.0 or above). These will be captured at every patient visit to the study center.
- Liver function tests.
- Complete blood counts.
- Concomitant medications
- Vital signs (temperature, blood pressure, pulse rate, and respiratory rate).
- Physical and neurological examinations.

Collection and monitoring of these data are detailed in [Sections 6.2.1 through 6.2.5 of the protocol](#).

### **11.2. Adverse Event Preferred Term and Body/Organ System Summary Tables**

Treatment Emergent Adverse Events (TEAEs) are defined as AEs that first occurred or worsened after the first administration of the investigational product. Adverse events are considered treatment-related if the relationship to study drug is related. A missing relationship will be imputed as related to study drug and included in the summary.

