- Day 7 (Visit 4): Patients will return to the study center to evaluate medical status (seizure diary, vital signs, and neurological exam), clinical laboratory assessments, concomitant medications, height/weight, and assess AEs. For those patients who tolerate the increased doses, the dose of vigabatrin will be increased to 150 mg/kg/day and CBD or CBD placebo to 40 mg/kg/day BID for the remaining 9 days. Vigabatrin, CBD, and matching placebo will be administered in a twice daily fashion at 12-hour intervals with meals.
- As part of their standard of care, investigators will assess safety and tolerability of the treatment regimens throughout the study period. All subjects will continue treatment until confirmation from the central reader on the 24-hour video EEG and clinical laboratory results are received.

Extended Treatment Period

Following the Initial Treatment Period:

- Complete Responders will continue receiving their assigned treatments of vigabatrin plus either CBD 40 mg/kg/day or matching placebo for 75 days, until Week 13 (Day 90) to monitor treatment response.
- During the Extended Treatment Period, the investigator may reduce the dose of CBD or CBD placebo to 30 mg/kg/day for safety or tolerability. If the subjects cannot tolerate the 30 mg/kg/day, they will be discontinued from the study following the completion of the taper period.

Partial Responders:

Partial responders will be offered the opportunity to enroll in an open-label safety study that allows investigators to combine standard-of-care treatment with CBD.

Taper Period

Following the completion of the Initial Treatment Period (Visit 6), partial responders who do not enroll in the open-label safety study and non-responders will have vigabatrin and CBD or CBD placebo tapered as follows:

- Vigabatrin taper: 150 mg/kg/day will be reduced to 100 mg/kg/day for 3 days, then the 100 mg/kg/day dose will be reduced to 50 mg/kg/day for 3 days, and then discontinued.
- CBD or CBD Placebo taper: 40 mg/kg/day will be reduced to 30 mg/kg/day for three days, then 30 mg/kg/day will be reduced to 20 mg/kg/day for 3 days, and then discontinued.

Complete Responders will be tapered off vigabatrin and CBD at the completion of the Extended Treatment Period, and all patients will be tapered off at any Early Withdrawal Visits, using the same schedules as described above.

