3. INVESTIGATIONAL PLAN

3.1. Overall Study Design

This is a Phase 3, double-blind, placebo-controlled, randomized, multicenter study to evaluate the efficacy, safety, and tolerability of Cannabidiol Oral Solution (CBD) as adjunctive therapy with vigabatrin as initial therapy, compared to vigabatrin alone in the treatment of infants newly diagnosed with Infantile Spasms (IS). Randomization will occur during Visit 2 and then allocated to one of two treatment groups:

- Treatment with vigabatrin plus
- CBD 40 mg/kg/day, or
- Matching CBD 40 mg/kg/day placebo

Approximately, 190 patients in total will be enrolled into one of the two treatment arms; 130 patients in the investigational product arm with 60 patients in the placebo arm. Patients will be dosed approximately every 12 hours with meals to help ensure consistent plasma levels are achieved and to reduce variability.

Doses of CBD exceeding 40 mg/kg/day will not be examined in this study. In addition to the safety assessments required by the study protocol, the investigator will monitor patients throughout the study as recommended in the approved product label for vigabatrin. Study participants will be newly diagnosed pediatric patients age 1 to 24 months (inclusive) experiencing infantile spasms who satisfy all inclusion/exclusion criteria. This study will be comprised of five periods: Screening, Initial Treatment, Extended Treatment, Taper, and Follow-up Periods, with a maximum duration of approximately 140 days.

The study design and patient progression through the study is outlined in [Figure 1](#). All screening, efficacy, and safety evaluations will be performed according to the schedule of assessments summarized in [Table 1](#).

Each newly diagnosed patient with Infantile Spasms will complete a Screening Period and will have up to 14 days to enroll in the study.

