3.1.2. Extended Treatment Period

Following the Initial Treatment Period:

- Complete Responders will continue receiving their assigned treatments of vigabatrin plus either CBD 40 mg/kg/day or placebo for 75 days, until Week 13 (Day 90), to monitor progress for treatment response.
- During the Extended Treatment Period, the investigator may reduce the dose of CBD or CBD placebo to 30 mg/kg/day for safety or tolerability. If the subjects cannot tolerate the 30 mg/kg/day, the drug will be discontinued and the patient withdrawn from the study following the completion of the taper period.

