4.5. Selection and Timing of Dose for Each Patient

Patients will receive vigabatrin and CBD or CBD Placebo twice daily during the 15-day Initial Treatment Period as described in [Section 4.1](#). Subsequently, Complete Responders will receive CBD or CBD Placebo and/or vigabatrin twice daily during the 75-day Extended Treatment Period.

The date and time of all investigational product administrations will be documented in the case report form (CRF).

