8.4.4.1. Adverse Events

The Medical Dictionary for Regulatory Activities (MedDRA, version 20.0) will be used to classify all AEs. Adverse event summaries will include only treatment-emergent AEs (TEAEs) by treatment group. Treatment-emergent adverse events (TEAEs) are defined as AEs that first occurred or worsened during the indicated treatment phase.

The number and percentage of patients with TEAEs will be summarized by system organ class (SOC) and preferred term (PT). Summaries of AEs by severity and relationship to the study treatment will also be provided. Serious adverse events (SAEs) and AEs resulting in discontinuation will be summarized separately in a similar manner. Patient listings of AEs and SAEs will be produced.

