#### **11.2.1. Summaries of Adverse Event Incidence Rates for All Subjects**

Overall summary of TEAE's will be summarized by any TEAE, treatment-related TEAE, treatment-related and severe TEAE, TEAE leading to study drug discontinuation, any serious TEAE, any serious and treatment related TEAE and TEAE resulting in death. Summaries of AEs will include incidence of TEAEs and treatment-related TEAEs by MedDRA preferred term (PT) and system organ class (SOC). The TEAEs will also be summarized by severity, PT, and SOC. Subjects reporting more than one TEAE are counted once in each category at the maximum severity.

AEs with a start date during the study will be summarized. Listings of all AEs, AEs leading to discontinuation of the study, SAEs, and deaths, if any, will be provided.

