## 14.2. Sample Table of Contents for Data Display Summaries

Title		Population	Comments
Study Population Section			
9.1.1	Summary of Subject Disposition	Randomized	Unique
7.4.1	Summary of Analysis Populations	Randomized	Unique
10.1.1	Summary of Demographic Characteristics	Safety	Unique
10.1.2	Summary of Demographic Characteristics	ITT	Repeat 9.3.1
Efficacy Section			
Figures			
11.7.1	Correlation between trough plasma drug levels and response	ITT	Unique
11.6.2		ITT	Unique
Tables			
11.6.1	Summary of Complete Responders	ITT	Unique
11.7.1	Summary of Partial Response – absence of spasms	ITT	Unique
11.7.2	Summary of Partial Response – absence of hypersarrhythmia	ITT	
11.7.3	Summary of Investigator CGI-I at End of Study/Early Withdrawal	ITT	Unique
13.1	Median Reduction in Seizure Burden and Percent of Spasm-Free Days	ITT	Unique
		ITT	Unique
Safety Section			
12.3.1	Summary of Exposure to Dronabinol Oral Solution by Treatment Group	Safety	Unique
12.2.1	Summary of Adverse Events by Treatment Group	Safety	Unique
12.2.2	Summary of Death and Serious Adverse Events by Treatment Group	Safety	Unique
12.2.4	Summary of Drug-Related Adverse Events by Treatment Group	Safety	Unique
12.6.1	Listing of Subjects Who Became Pregnant During the Study	Safety	Unique
12.6.2	Summary of Actual Values and Changes from Baseline in Clinical Chemistry Data by Treatment Group and Study Time	Safety	Unique
12.6.3	Summary of Actual Values and Changes from Baseline in Hematology Data by Study Time	Safety	Unique
12.7.1	Summary of Actual Values and Changes from Baseline in Vital Signs by Treatment Group and Study Time	Safety	Unique
12.8.1	Summary of Physical Examination Results		
12.9.1	Summary of ECG Data	Safety	Unique

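### The SAP reports TEAEs as crude percentages by arm over all time after first dose, although under the protocol time at risk depends on complete response, so the main AE comparison can show an excess on CBD from longer observation alone

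*SAP*

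**What the plan says.** **SAP.** Section 11.2 defines TEAEs as "AEs that first occurred or worsened after the first administration of the investigational product". It names a start but no end, and no phase. Section 11.2.1 adds that "AEs with a start date during the study will be summarized" and counts a subject once in each category, which is crude incidence. The sample table list in 14.2 has one "Summary of Adverse Events by Treatment Group" and no version by period. Section 11.3 summarises duration of exposure by arm, but nothing in the SAP uses it as a denominator for AEs.

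**Protocol.** Section 8.4.4.1 defines TEAEs as "AEs that first occurred or worsened during the indicated treatment phase". All patients are dosed "twice daily during the 15-day Initial Treatment Period" (4.5). After that, section 3.1.2 states: "Complete Responders will continue receiving their assigned treatments of vigabatrin plus either CBD 40 mg/kg/day or placebo for 75 days". Under 3.1.4, non-responders, and partial responders who do not enter the open-label study, are tapered after Visit 6.

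**A conflict between the two.** SAP 3.1 and 4.3 continue partial as well as complete responders, for 76 days. The SAP states that it is based on the protocol dated 30 October 2017 (V2.0).

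**The concern.** Under the protocol, how long a patient is observed for AEs is a consequence of the primary efficacy outcome. A complete responder has about 75 more days on drug than anyone else. If CBD raises the complete response rate, more of its arm stays in the long-observation group. A crude percentage with any TEAE then tends to be higher on CBD even when the AE rate per day is identical in the two arms.

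Safety and tolerability is a stated secondary objective, and AE percentages by arm are the main result that readers will use to judge it. As specified, that result mixes any real AE effect with the efficacy effect, and the distortion counts against CBD just when CBD works. The protocol's phase-based definition would allow a comparison over equal planned time, but the SAP does not carry it over.

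**Working it through.** **Inputs from the protocol.** Screening: patients "will have up to 14 days to enroll in the study" (3.1). Initial treatment 15 days (4.5). Extended treatment 75 days (3.1.2). Taper 3 + 3 = 6 days (3.1.4). Follow-up call 30 days after stopping drug (3.1.5). Assumed complete response 60% with CBD and 40% without (8.2).

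**The protocol's own figure.** 14 + 15 + 75 + 6 + 30 = 140 days, which matches its stated maximum duration of approximately 140 days.

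**Time per patient.**
- On drug including taper: complete responder 15 + 75 + 6 = 96 days; others 15 + 6 = 21 days.
- Including follow-up: 96 + 30 = 126 days and 21 + 30 = 51 days.

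**Mean time per arm** = p × long + (1 − p) × short, where p is the complete response rate.
- On drug with taper: CBD 0.6 × 96 + 0.4 × 21 = 66; placebo 0.4 × 96 + 0.6 × 21 = 51; ratio 1.29.
- With follow-up: CBD 0.6 × 126 + 0.4 × 51 = 96; placebo 0.4 × 126 + 0.6 × 51 = 81; ratio 1.19.

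**Crude incidence.** The documents give no AE rate. Assume one constant rate h, the same in both arms and throughout. The share with any TEAE is p(1 − e^(−h × long)) + (1 − p)(1 − e^(−h × short)). The difference between arms is therefore 0.2 × (e^(−h × short) − e^(−h × long)).

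| h per 100 patient-days | On drug + taper: CBD vs placebo | Excess (points) | With follow-up: CBD vs placebo | Excess (points) |
|---|---|---|---|---|
| 0.5 | 26.9% vs 21.2% | 5.6 | 37.0% vs 32.2% | 4.8 |
| 1 | 44.6% vs 36.0% | 8.6 | 59.0% vs 52.6% | 6.3 |
| 2 | 64.9% vs 54.7% | 10.2 | 80.7% vs 75.1% | 5.6 |

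For example, at h = 0.01 on drug with taper: 0.2 × (0.8106 − 0.3829) = 0.086. The follow-up columns apply the same rate off drug. If events are rarer off drug, the result lies nearer the first pair of columns.

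**Sensitivity.**
- *Equal response* (40% in each arm): the excess is 0.
- *Early clustering*: with a 15-day risk of 20% and a later hazard of 0, 10, 25, 50 or 100% of the initial one, the excess (on drug with taper) is 0, 1.7, 3.8, 6.5 or 9.8 points.
- *The SAP's design*: 14 + 76 + 3 = 93 days for those who continue and 14 + 3 = 17 for the rest, with 62% vs 40% response. With no partial responders, mean time is 64.1 vs 47.4 days, ratio 1.35. With partial response of 10% or 20% in each arm, the ratio is 1.30 or 1.27. If CBD only converts partial into complete responses (partial response 0% vs 20%), 62% and 60% continue and the ratio is 1.02.

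**Check of the remedy.** Over the first 15 days at h = 0.01, incidence is 1 − e^(−0.15) = 13.9% in both arms. Events per 100 patient-days are 1 in both arms. Either measure removes the spurious difference under the constant-rate assumption.

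**The case against.** Several points on the other side stand.

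- **Window.** A reader might contrast 90 with 15 days of treatment, giving means of 60 vs 45 days and an excess of 5.8, 9.1 or 11.5 points at the three rates above. That leaves out the taper and follow-up, when AEs are still collected and which the SAP's open-ended window includes. The figures in the working are the ones to use.
- **Constant hazard.** Both drugs are titrated over the first week, so AEs may cluster early and the excess may be small. The working also assumes that every complete responder reaches Day 90, although withdrawal is allowed at any time, and that everyone else completes taper and follow-up.
- **Who continues.** Under the SAP's rule the imbalance depends on partial-response rates that neither document gives. A reader might infer that the CBD arm must show more AEs whenever CBD works. That does not follow under the SAP's rule.
- **Other safety data.** A reader might infer that every safety comparison is affected. It is not: SAP 11.5, 11.6 and 11.8 summarise laboratory values, vital signs and neurological shifts by visit. Exposure by arm is also reported, so the imbalance would be visible, and all safety analysis is descriptive, so no error rate is at stake.
- **Protocol wording.** Section 8.4.4.1 does not name the phases or promise tables by phase, and 6.2.6.1 starts TEAE monitoring at first dosing, which fits the SAP. The SAP's table list is a sample, and the SAP says it may change with protocol amendments.

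None of this supplies an end of window, a split by period or an exposure-adjusted rate for AEs, and these are what the comparison lacks.

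**Conclusion.** The point holds in a limited form. SAP 11.2 and 11.2.1 report crude TEAE incidence over an open-ended window and drop the phase restriction in protocol 8.4.4.1. Under the protocol's continuation rule, time at risk depends on complete response, so a higher response rate on CBD will tend to raise its TEAE percentage at an unchanged AE rate.

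At 60% vs 40% response and a common constant rate of 0.5 to 2 per 100 patient-days, the spurious excess is about 5.6 to 10.2 points on drug with taper, or 4.8 to 6.3 points with follow-up included. The AE rate is an assumption. The excess falls to zero if all AEs occur in the first 15 days or if response is equal, and it could nearly vanish under the SAP's continuation rule.

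The documents do not support a claim that an excess on CBD is certain, or that all safety comparisons are confounded. The main AE comparison is affected, and the primary analysis is not. The SAP should be corrected before database lock.

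**What to change.** 1. Align SAP 11.2 with protocol 8.4.4.1: name the treatment phases and state the day on which the TEAE window ends.
2. Tabulate TEAEs by period. Make the 15-day Initial Treatment Period the main comparison by arm, since all randomised and treated patients have equal planned exposure there.
3. Show the Extended Treatment Period separately, labelled as a non-randomised comparison, because it includes only continuing responders, a group selected after randomisation. Show Taper and Follow-up separately too.
4. Add events per 100 patient-days to any whole-study AE table, beside the period tables and not in their place. If all AEs fell in the first 15 days, equal event counts divided by 66 and 51 days would give a CBD-to-placebo rate ratio of 51/66 = 0.77, an error in the other direction.
5. Reconcile the protocol and SAP on who continues after the Initial Treatment Period and for how long, and define the AE periods to match.

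The cost is a few extra tables, built from AE onset dates and dosing dates that are already collected.
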